a) Negative and cognitive symptoms. We hypothesize that negative symptoms and cognitive impairment (measured by BPRS subscales) will correlate negatively with weight loss. Motivation (measured by the URICA) and illness insight (measured by the SAIQ) will be positively correlated with weight loss.

b) Treatment adherence. SMI veterans involved in the Lifestyle Balance Program will have better adherence to psychiatric treatment than the "usual care" group as measured by a treatment adherence questionnaire, percent of antipsychotic medication refills and percent of appointments attended.

c) Ongoing informed consent. Consent is to be an ongoing process and we hypothesize that SMI veterans involved with the program will continue to give informed consent to participate. This will be demonstrated by subjects' performance on the informed consent quiz at 0, 6, and 12 months of participation.

II. Background and Significance

A. Overview of Obesity in the SMI Population: [Definitions: "Obesity" is defined as a body mass index of ≥ 30 . "Overweight" is defined as a body mass index of ≥ 25 . Body mass index (BMI) is a ratio of person's weight in kg divided by their height in meters squared. Severe mental illness (SMI) includes schizophrenia, bipolar disorder, severe recurrent depression, obsessive-compulsive disorder, and panic disorder] Obesity is a severe public health problem in the United States that shortens our lives due to its association with a number of diseases, including diabetes, cardiovascular illness, and several forms of cancer

(4). Obesity is “outweighing” smoking as the number one modifiable risk factor for cardiovascular disease and death in this country. Obesity is an even greater problem for patients with SMI. The SMI have a higher all-cause mortality rate than the normal population with suicide and cardiovascular disease accounting for the lion’s share of the early deaths (5-7). Given a smoking prevalence sometimes exceeding 75% it is not surprising that cardiovascular disease remains the leading cause of premature deaths.

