Initial inter-rater reliability will be maintained for the BPRS, CGI, Ham-D, and QOLS scales by utilizing recordings of taped live interviews -available by DVD - that all raters must assess during the initial start up phase and every 6 months thereafter. Initially each rater will assess 3 tapes and kappa will be determined for inter-rater reliability. Once the study is underway, to prevent rater drift, every 6 months all raters will rate a recorded interview that will be made available to them by DVD.

Inclusion/Exclusion Criteria: Patients recruited for this research study from four different sites will need to commit to a 12 month period of participation. This protocol will have two phases, an initial 2-month intensive phase (weekly classes and individual visits) followed by a 10 month (once per month) maintenance extension phase. Since many patients with SMI live somewhat transient existences, patients included in this study cannot be homeless and must have some type of stable living circumstance. All patients with SMI (e.g. psychotic disorders, schizophrenia, schizoaffective disorder and bipolar illness, post traumatic stress disorder) aged 18-70 who are taking antipsychotic medications, admitted to inpatient wards of the Greater Los Angeles VA Medical Center, Long Beach Medical Center, as well as outpatient programs at all four sites, of the Sepulveda VAMC, and the Los Angeles Ambulatory Care Center, West Los Angeles VA Mental Health Clinic, Schizophrenia Treatment Unit, Domiciliary, Exodus Lodge, and local Board & Cares and residential dual diagnosis treatment programs will be screened for possible participation in this behavioral weight loss program that includes diet, exercise, and Lifestyle Balance classes. We intend to recruit non-veteran females (to increase our representation of females in this research) from the Didi Hirsch Community Mental Health Center, in addition to our women's clinic here at West Los Angeles. Sepulveda VAMC has a large outpatient program, and a partial hospitalization program (that is converting to a PRRC) and MHICM programs from which to recruit patients. LAAC also has a large outpatient mental health program and 3 day treatment/partial hospitalization

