Lifestyle Balance Coaches and physicians will meet as a team to discuss patients who need additional interventions to meet their expected dietary changes and exercise goals. We have developed a flow chart that our Lifestyle Balance Coaches will utilize to assist patients with adherence to the program. The number and types of interventions required to assist patients in making healthy lifestyle changes will be tallied. For the most part, these are the modalities described in the grant that can be ascertained in an objective manner for data analysis purposes. Lifestyle coaches' adherence to the training program will be assessed by a simple fidelity measure and an independent objective consultant who will randomly observe coaches meeting with veterans in the lifestyle balance intervention group.

Because weight gain can be a deterrent for patients to adhere to antipsychotic medications, one of our hypotheses is that people in the lifestyles intervention group will have higher rates of adherence to their psychiatric medications than patients in the "treatment as usual" group. We will rely primarily upon the VA computerized record system to determine the percent of psychiatric appointments attended by patients as well as the percent of medications refilled. In addition, we have developed and will utilize several objective measures of adherence to treatment.

J. Additional Interventions: In the event that the patient is not losing weight or is unable to adjust to their diet or exercise regimen, we will request the patients permission for additional intervention so that we may assist them adhere to their exercise and diet. Additional interventions are optional and may include:

1. Additional Exercise Interventions

- a. The research physician will review the patient's medical chart to determine if their current medications may be contributing to fatigue, sedation, and/or lack of motivation. Consultation with the patient's treating psychiatrist may lead to suggestions about medication adjustments to be made by the treating psychiatrist (as it would be done in usual care) to optimize energy and motivation of patients.
- b. The patient's rewards may be adjusted to optimize their motivation to exercise (See DPP Toolbox Appendix).
- c. The patient's exercise goal expectations may be adjusted.

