Analysis plan: We do not expect to see meaningful weight loss in the usual care group, and thus do not expect meaningful correlations based on these hypotheses. Accordingly, the primary tests of each of these hypotheses will be done by computing Pearson correlations between the specified variables within the treatment group. Supplementary analyses will be done within the context of the mixed effects designs described above, including these variables as possible treatment effect moderators. Separate analyses for hypotheses (i.) through (iv.) above will be done to examine possible interactions of each of these variables considered separately with treatment group. These analyses will test whether treatment may be more or less effective as a function of these variables (negative symptoms, motivation to change, cognitive cluster, insight). If so, we will stratify the groups according to these variables to simplify presentation of the results, e.g., treatment outcomes presented separately in groups with more versus less cognitive impairment).

b) SMI patients involved in the Lifestyle Balance Program will have better adherence to psychiatric treatment than the Usual Care group as measured by percent of psychotropic medication refills and percent of appointments attended.

Analysis plan: We will compute these dependent measures (percent of psychotropic medication refills and percent of appointments attended) to create summary scores within each of the three study follow-up epochs (baseline- 8 weeks, 8 weeks- 6 months, 6-12 months). These will be analyzed using general linear mixed effects models with repeated measures, including baseline stratification medication as a covariate. We will test group, time and interaction effects, and perform between-group contrasts for each time period.

To determine what patient characteristics, e.g. Medication group, diagnostic or symptom status is most conducive to positive outcome we will use classification analysis using the recursive partitioning algorithm to determine which patient characteristics at baseline are the best predictors for positive outcomes. Recursive partitioning is a computationally intense data mining technique that allows for the analysis of multiple predictors simultaneously while protecting against type I error inflation due to multiple testing and it provides non-parametric confidence intervals by using cross-validation (75).

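### Secondary hypothesis (b) is stated on antipsychotic refills and a questionnaire, but its analysis uses psychotropic refills, omits the questionnaire and takes no pre-randomisation adherence value

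*Combined protocol and SAP*

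**What the plan says.** Three places describe how adherence is measured, and they differ.

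- Section I.D.2(b) uses a "treatment adherence questionnaire, percent of antipsychotic medication refills and percent of appointments attended".
- Section V.I starts from weight gain as a deterrent to taking antipsychotics, then predicts "higher rates of adherence to their psychiatric medications". For appointments and refills it says "We will rely primarily upon the VA computerized record system", and it adds that several further objective measures, which it does not name, will be used.
- Section V.N.4, Secondary Hypotheses (b), restates the hypothesis and its dependent measures as "percent of psychotropic medication refills and percent of appointments attended". No questionnaire appears.

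The V.N.4(b) model summarises these percentages within "three study follow-up epochs (baseline- 8 weeks, 8 weeks- 6 months, 6-12 months" and fits a mixed model "including baseline stratification medication as a covariate". It tests group, time and interaction effects, with a between-group contrast in each period.

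On the population, section V.A describes 120 veterans, while the Inclusion/Exclusion text says "We intend to recruit non-veteran females", from a community mental health center among other sources, and gives no number.

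**The concern.** The rationale is about antipsychotics: if the programme limits weight gain, patients have less reason to stop the drug that causes it. A psychotropic refill percentage also counts drugs outside that rationale. The stratification text itself names mood stabilizers as co-medication. No section says which definition governs, so the refill measure could be settled after the data are seen. Section V.N.1 answers concerns about Type I error by pointing to well-specified dependent variables, and this one is not well specified.

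Two further gaps follow from the same paragraph. A measure named in the hypothesis has no stated analysis. And the model uses no adherence value from before randomisation, although adherence data are already to be drawn from a record system. Finally, if record-based percentages cannot be obtained for non-veterans, the plan does not say who is in the analysis.

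**Working it through.** **Wording, side by side**

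| Section | Refill measure | Appointments | Questionnaire |
|---|---|---|---|
| I.D.2(b) | antipsychotic | yes | yes |
| V.I | psychiatric medications | yes | not named; other unspecified measures |
| V.N.4(b) | psychotropic | yes | no |

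The Schedule of Events lists a Treatment Adherence Log at baseline, 8 weeks, 6 and 12 months. The documents do not say whether this is the questionnaire of I.D.2(b), and the V.N.4(b) model does not use it.

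**The plan's own power figure.** Section V.N.5 gives no power for adherence. Its general statement takes f = 0.25, two-sided alpha 0.05, 120 × (1 − 0.45) = 66 completers, m = 4 time points and within-subject r = 0.50. For the between-group effect:

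λ = f²·N·m / (1 + (m − 1)r) = 0.0625 × 66 × 4 / 2.5 = 6.6, with df 1 and 64. Power is 0.716 against 0.7199 stated, so the figure reproduces.

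**The same inputs with the three adherence epochs.** λ = 0.0625 × 66 × 3 / 2 = 6.19, power 0.688. This borrows f = 0.25 and r = 0.50 for illustration; the documents give neither for adherence.

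**Adding a pre-entry covariate.** Let b be its correlation with each epoch. The documents give no value, so 0.3 to 0.7 is assumed.

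- Single-epoch contrast: the variance falls by b², which is 25% at b = 0.5 and 49% at 0.7. The sample-size equivalent is 1/(1 − b²) − 1, or 33% and 96%.
- Average over three epochs: the variance of a patient's mean is (1 + 2 × 0.50)/3 = 0.667, and the covariate removes b² of it.

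| b | Remaining variance | Ratio | Reduction | Power (from 0.688) |
|---|---|---|---|---|
| 0.3 | 0.577 | 0.865 | 13.5% | 0.750 |
| 0.5 | 0.417 | 0.625 | 37.5% | 0.872 |
| 0.7 | 0.177 | 0.265 | 73.5% | 0.997 |

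The last row should be read with caution: it has the pre-entry value predicting each epoch better (0.7) than the epochs predict each other (0.50).

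- Group-by-time: this rests on differences between epochs. If b is the same for every epoch, the covariate is uncorrelated with those differences and the gain is zero.

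**Record coverage.** The number of non-veterans is not stated. If 5%, 10% or 20% of the 66 had no record-based value (assumed shares, leaving 63, 59 or 53), the power of 0.688 would become 0.667, 0.638 or 0.590.

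**The case against.** The best defence is that both statements of the hypothesis concern adherence to psychiatric treatment as a whole, with refills as an indicator. Section V.I itself moves from antipsychotics to psychiatric medications generally. All participants take antipsychotics, so those refills sit inside the wider measure. That is fair: the two measures overlap. It does not tell the analyst which one to compute.

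On the questionnaire and baseline, V.N.4 has a general sentence applying repeated measures at baseline, 8 weeks, 6 and 12 months to all treatment-effect hypotheses, and the log is scheduled at exactly those times. This is a plausible route. But the sentence sits under the primary hypotheses, it does not name the log, and hypothesis (b) has its own plan built only on follow-up epochs.

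On the covariate, omitting it does not bias a randomised comparison. That stands in full. The propensity scores in V.N.1 do not fill the gap, because they enter only if the groups differ significantly at baseline, and adherence is not named among the characteristics compared.

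Two practical objections also stand. Recruitment includes inpatient wards and residential programmes, so a prior outpatient percentage may be undefined or unrepresentative for some patients. And the documents do not state that the record system holds usable history for each veteran. The fix therefore has to say what happens when no pre-entry value exists.

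**Conclusion.** The point holds as an inconsistency in the outcome definition, an unanalysed measure and an avoidable loss of precision on a secondary hypothesis. The inconsistency rests on the text alone. The precision gain rests on assumed correlations and depends on the contrast: 25% to 49% of variance for a single epoch at 0.5 to 0.7, about 37.5% for the three-epoch average at 0.5 with within-subject r = 0.50, and none for group-by-time under equal correlations.

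A reader might infer more, and the documents do not support it:

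- That the psychotropic measure dilutes the effect. This is plausible under the rationale, but no figures separate antipsychotic from other refills.
- That the trial gives up the equivalent of 33% to 96% more patients. Those figures apply only to single-epoch contrasts at assumed correlations.
- That non-veterans would be scored as non-adherent. Nothing in the plan codes an absent record as zero, and its mixed models permit missing data.
- That non-veterans certainly have no VA record. This is an inference. Section V.I says the records are the primary source, not the only one, and I.D.2(b) words the hypothesis for veterans, whereas V.N.4(b) says patients.

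The coverage gap is therefore a missing rule of unknown size.

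**What to change.** In V.N.4, Secondary Hypotheses (b):

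1. Name percent of antipsychotic refills as the analysed refill measure, matching I.D.2(b) and the rationale in V.I. Keep all psychotropics as a supportive analysis, and align the wording in the three sections.
2. State whether the Treatment Adherence Log is the questionnaire, and analyse that instrument at 8 weeks, 6 and 12 months with its baseline value in the model.
3. Add pre-entry refill and appointment percentages from the VA record system as covariates, over a window fixed in advance. Use a missing-value indicator for patients with no usable prior outpatient record, applied identically in both arms.
4. Report record-based adherence for patients receiving VA care, defined by status at entry so that the randomised comparison is kept. Treat other patients as missing for these two measures and report how many there are.

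The cost is SAP wording and one further extract from a system already in use. The downside is that some patients will have no pre-entry value and will contribute little to the precision gain. No visit, assessment or treatment changes.

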The aims of this research program are to 1) reverse obesity in patients with severe mental illness who take antipsychotic medications and 2) begin to disseminate the program to non-research mental health settings such as Psychosocial Rehabilitation and Recovery Centers (PRRCs). It is crucial to the VA mission to develop an accessible and effective program tailored to veterans with severe mental illness (SMI) given the significant morbidity and treatment challenges in this population. Though the existing MOVE! program is recommended for weight loss for all veterans, many patients with SMI are unable to participate for a variety of reasons. Thus, this program addresses a gap in current care. The program in this proposal is similar to MOVE!, but is

specifically designed to meet the needs and treatment challenges of veterans with SMI, and particularly antipsychotic medication associated obesity, over a longer treatment period. Because patients with SMI must take antipsychotics their entire lives, we must be constantly vigilant and monitor their weight and other metabolic parameters as now mandated by the FDA and Inspector General for the VA.

B. Short Term Objectives: The primary objective of this prospective, multi-site randomized, parallel group research proposal is to evaluate the effectiveness of a multi-modal intervention to combat antipsychotic associated obesity, and to prevent and monitor diabetes and other metabolic side effects of atypical antipsychotics in SMI patients. Specifically, we wish to test the effectiveness of a lifestyle intervention program targeting healthy lifestyles in four different VA settings. We will determine if the classes, individual coaching, along with a prescribed diet and exercise regimen improve patients' metabolic profiles, cardiovascular risk factor status, and overall mental health compared to usual psychiatric treatment. Further, this program will provide the opportunity to increase our ability to identify which veterans (based upon diagnostic, medication, and psychosocial status) are most likely to benefit from this behavioral weight loss intervention.

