3. Repeated measures analyses: We propose to longitudinal (repeated measures) analyses to maximize the additional power we gain by observing the same subjects across 12 months.. Repeated measures analyses permit contrasts at each time point, and also describe and compare trajectories of change (trends), speed and durability of effects. We will also conduct separate cross-sectional to provide outcome data for ongoing safety review, interim progress reports, study oversight and conduct.

The primary design for longitudinal (repeated measures) analyses of continuous outcome scales will be a 2-group (treatment) mixed general linear model of timepoints nested within participants. This is very general linear model that permits flexibility in specifying the nature of the covariances among the dependent measures, allows time-dependent, within and between subject covariates, and permits incomplete (i.e., missing) data. Analyses of trends across the monthly assessments will be done using growth curve model within the mixed model analysis of covariance design with repeated measures described above. We propose to model a linear trend of time unless inspection clearly suggests nonlinearity. By fitting a slope over time (and intercept) for each participant who has baseline and at least one other measure, this method makes good use of all the data, and is robust even if some of the some measures are missing. The use of the mixed general linear model for all cross-sectional and linear hypotheses ensures that results will be comparable across different analyses and provide a framework to include group, person and time-specific covariates if it becomes necessary. The preliminary analyses have shown that this analysis strategy provides meaningful results even with partial data and suggests that we will exceed the originally projected power.**4. Stratification:** Randomization will be stratified by type of antipsychotic and presence of mood stabilizer medication (e.g., depakote, lithium) to assure balance on olanzapine and clozapine by randomizing within three strata – olanzapine, clozapine, and all other antipsychotics -- using three separate randomization lists. Because such stratification can adversely affect statistical power by creating artificially comparable (and heterogeneous) groups, two dummy variables coding olanzapine and clozapine at baseline will be included in all analyses as covariates.

4. Statistical Plans:

Primary Hypotheses:

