It provides valid statistics even in cases where there are more potential predictors than observations, and allows us to include all demographic, psychosocial, psychiatric and medical data known at baseline as potential predictors. The results of this analysis will suggest which patients are most likely to profit from further interventions, and it will also characterize the most at risk patients.

c) Subjects will continue to give meaningful, informed consent to participate throughout the study. They will see no significant decrease in their score on the informed consent quiz given every 6 months.

Analysis plan: A general linear model (GLM): ANOVA will be performed to compare the informed quizzes score results at 0, 6, and 12 months during the subjects' participation in the study.

5. Power Analysis: All calculations are based assuming a conventional medium effect size ($f=.25$, Cohen 1988); and a two-tailed alpha set at 0.05. Tuomilehto et al. estimated the SD of weight loss at roughly 5 kg across several treatment conditions (lifestyle changes vs. control) (76). A medium effect would thus translate into a group difference of about 2.5 kg or about 5.5 pounds. With an enrollment of $N=120$ and an estimated attrition rate of 45% we expect that at least 66 subjects will provide complete the study and provide 4 data points. The power analyses below are based on a sample size of $N=66$, i.e. this is a very conservative estimate due to the fact that the mixed linear model allows us to include cases with missing values in the analyses and that while they don't provide as much information as complete cases they still provide some information and will increase power. For the between-group comparisons, $N=66$ yields power=.7199 for main differences between groups if we assume that the within subject correlation is $r=.50$. Power to test for the difference in outcome trajectories of time – our main outcome variable is 0.99, and even if the effect is as small as $f=0.15$ we will have sufficient power to distinguish between the trajectories of the two treatment groups (power=0.83) insuring that we will get significant, insuring that we Preliminary data analyses shows that these assumptions are quite conservative and that effect sizes seem to be slightly larger than projected, suggesting that the final power will exceed the estimates presented here.

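### The recursive partitioning looks for predictors of a good outcome, so it cannot support the stated conclusion about who profits from the program

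*Combined protocol and SAP*

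**What the plan says.** Section I.B (Short Term Objectives) includes identifying, by diagnostic, medication and psychosocial status, which veterans "are most likely to benefit from this behavioral weight loss intervention".

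The analysis offered for this is in section V.N, Statistical Plans, after the analysis plan for secondary hypothesis (b). Medication group and diagnostic or symptom status are its examples. Recursive partitioning is to be used "to determine which patient characteristics at baseline are the best predictors for positive outcomes". The candidates are described as wide enough to "include all demographic, psychosocial, psychiatric and medical data known at baseline as potential predictors". The conclusion follows: "The results of this analysis will suggest which patients are most likely to profit from further interventions". The same sentence adds that the analysis will characterise the patients most at risk.

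Moderator tests appear separately, in the analysis plan for secondary hypothesis (a). Supplementary mixed models will "examine possible interactions of each of these variables considered separately with treatment group". The variables are negative symptoms, motivation to change, the BPRS cognitive cluster and insight. Medication enters the models differently. The Stratification paragraph says that "two dummy variables coding olanzapine and clozapine at baseline will be included in all analyses as covariates", and states no interaction of these with treatment.

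**The concern.** Benefit is a contrast: a patient's expected outcome in the program minus the same patient's expected outcome under usual care. A tree that splits on outcome finds characteristics that go with doing well. Some of these may modify the program's effect; others may mark patients who would do well in either arm. The tree cannot tell the two apart, because nothing in its stated target or candidate list compares the arms.

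Medication is where confusion is most likely. Section II.C ranks the second generation drugs by weight-gain liability, so by the plan's own account medication is plausibly prognostic. The progress report (section IV.E.2(g)) speaks of patients profiting in the sense of a program effect that differs between medications. The new plan keeps that word but assigns medication and diagnosis to an analysis that does not estimate such a difference.

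At stake is one stated objective. The primary hypotheses are not affected.

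**Working it through.** **The plan's own figures.** No figure is given for the tree. The nearest are in the Power Analysis: N=66 completers, f=0.25, four time points, within-subject correlation 0.50 and "a two-tailed alpha set at 0.05".

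- Between groups: λ = N f² m / (1+(m−1)ρ) = 66 × 0.0625 × 4 / 2.5 = 6.6, with df 1 and 64. Power is 0.716 (stated 0.7199).
- Trajectories: λ = N f² m / (1−ρ), with df 3 and 192. At f=0.25, λ = 33 and power is 0.999 (stated 0.99). At f=0.15, λ = 11.88 and power is 0.828 (stated 0.83).

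The stated figures reproduce.

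**Can the tree find people who profit when benefit is equal?** From the plan: SD 5 kg and a group difference of 2.5 kg. Assumed: a 50/50 baseline trait adding 5 kg of loss in both arms, and a program effect of 2.5 kg for everyone. Mean losses are 0 and 5 kg (usual care, trait absent and present) and 2.5 and 7.5 kg (program). Call a loss above the overall median, 3.75 kg, a positive outcome.

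| | Trait absent | Trait present |
|---|---|---|
| Program | Φ((2.5−3.75)/5) = 0.401 | Φ((7.5−3.75)/5) = 0.773 |
| Usual care | Φ((0−3.75)/5) = 0.227 | Φ((5−3.75)/5) = 0.599 |
| Difference between arms | 0.174 | 0.174 |

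An outcome tree sees 77% against 40% in the program arm and would single out the trait. The benefit is the same in both columns, in kilograms and in proportion responding.

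**How often?** Simulated first Gini split on that binary outcome; ten 50/50 candidates (eight of them noise), 1:1 arms, residual SD 5 kg, 5,000 runs. All effect sizes are assumptions. Each cell gives N=66 / N=120.

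| Scenario | Trees fitted to | First split: prognostic trait | First split: true modifier |
|---|---|---|---|
| Prognostic 5 kg; constant effect 2.5 kg | Both arms | 87% / 98% | none exists |
| | Program arm | 64% / 85% | none exists |
| Prognostic 5 kg; modifier moves effect from 0 to 5 kg | Both arms | 77% / 91% | 11% / 7% |
| | Program arm | 41% / 47% | 39% / 46% |
| Prognostic 2.5 kg; same modifier | Both arms | 31% / 41% | 29% / 38% |
| | Program arm | 13% / 12% | 57% / 77% |

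The share choosing the true modifier runs from 7% to 77%, so no one error rate describes the plan.

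**What would a direct test of benefit deliver?** For a treatment-by-binary-moderator contrast at one endpoint, SE = 5 × √(2/(0.5Np) + 2/(0.5N(1−p))), where p is the share with the moderator. Power ≈ Φ(δ/SE − 1.96).

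| N | p | SE (kg) | Power, δ=2.5 kg | Power, δ=5 kg | δ for 80% power (kg) |
|---|---|---|---|---|---|
| 66 | 0.50 | 2.46 | 0.17 | 0.53 | 6.9 |
| 66 | 0.25 | 2.84 | 0.14 | 0.42 | 8.0 |
| 120 | 0.50 | 1.83 | 0.28 | 0.78 | 5.1 |
| 120 | 0.25 | 2.11 | 0.22 | 0.66 | 5.9 |

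These are for a single prespecified moderator. Searching many candidates would do worse. Repeated measures may do somewhat better than one endpoint.

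**The case against.** The best defence is that the tree may be meant for the program arm alone. The analysis plan for secondary hypothesis (a) runs its main correlations within the treatment group, because little weight loss is expected under usual care. On that premise, a good outcome in the program arm comes close to benefit. Part of this stands. The plan does not say that the arms are pooled, so a reader who infers pooling goes beyond the text. A program-arm tree also does better when prognosis is weak, as the last scenario shows.

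The premise does not rescue the conclusion. Little average change under usual care is not little variation between patients. Section IV.E.2(a) reports usual-care changes over six months from a 19-pound loss to a 29-pound gain. In the constant-effect scenario, the program-arm tree still split first on the prognostic trait in 64% to 85% of runs.

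It is also fair that the plan is not silent on moderators: four variables get interaction tests. Section V.L further promises post hoc examination of drug types, but specifies no interaction. The wording is cautious, and the claim about patients at risk is one that an outcome tree can support. These points narrow the concern to the claim about who profits, and to medication and diagnosis.

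Finally, the low interaction power is a real argument against expecting much from a benefit tree. It is no argument for reading an outcome tree as one.

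**Conclusion.** The concern holds: the analysis as described cannot support the conclusion drawn from it about who profits, and an objective in section I.B is left without a matching analysis for medication and diagnosis. This follows from the stated target of the tree and needs no assumption about effect sizes. The simulated frequencies do need them: only N, the SD and the 2.5 kg group difference come from the plan.

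Two stronger readings are not supported. One is that the tree would almost never find a true effect modifier. That depends on strong prognosis, pooled arms and how the modifier acts within each arm; under other reasonable assumptions the modifier is chosen most often. The other is that program places would go to the wrong patients. Nothing in the documents allocates places from this analysis.

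The tree is not a primary analysis, so this should be corrected but does not threaten the main comparison.

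**What to change.** 1. Limit the conclusion to baseline predictors of outcome and patients at risk, and drop the claim about who profits. Define positive outcome and state the arm or arms in which the tree is fitted. This is a text edit and is the sure remedy.
2. To address who benefits, add treatment-by-medication-group and treatment-by-diagnosis interactions to the mixed model already planned. Alternatively, use a tree that splits on the treatment-by-covariate interaction in both arms. Label either as exploratory, as the plan promises for exploratory analyses (section V.N.1).

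The second step costs a few model terms or another routine in R, which the plan already names. Its real limit is precision. The plan should therefore report interaction estimates with confidence intervals and say in advance that a null result would not show equal benefit.
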